With very few exceptions, most studies were characterized by high risk of bias in six bias domains (selection, performance, detection, attrition, reporting, other).¹⁴ Lack of randomization and blinding, and failure to explicitly define clinical outcomes contributed to these problems. The majority of studies used oral vitamin C supplementation. Oral doses, even those in excess of 200 mg, are associated with little or no clinically significant increases in circulating Vitamin C levels¹⁵, and pharmacokinetics of oral ascorbic acid dosing differs considerably from intravenous dosing.¹⁶ However most assessed studies reported positive effects of vitamin C supplementation. Meta-analysis of these papers indicated a significant overall reduction in both post-operative AF (9 studies; n= 1039 patients; odds ratio 0.37 [95% CI 0.28, 0.50]) and a small reduction in length of hospital stay (6 studies; n= 672 patients; mean difference -1.3 days [95% CI -1.6, -1.0]). A few papers reported measurements of isolated inflammatory and coagulation markers; however, results were equivocal. For example, vitamin C supplementation of CABG patients (usually in combination with various antioxidant cocktails) seemed to attenuate post-operative oxidative stress,¹⁷ myocardial “injury” (defined as a five-fold elevation of cardiac biomarker values and cardiac dysrhythmia),¹⁸ and endothelial dysfunction.¹⁹ In contrast, a study of cardiac surgery patients on or off CPB did not detect statistically significant differences between oral vitamin C and control groups in C-reactive protein (CRP) concentration, white blood cell (WBC) count, or fibrinogen concentration, markers of inflammation and coagulopathy.²⁰ However the study was underpowered because of early study termination, and data were uncorrected for non-normality, invalidating subsequent statistical analyses. In summary, although suggestive of benefit, current evidence of efficacy of high-dose vitamin C was of low quality with limited and/or irrelevant outcomes, necessitating development of more rigorous clinical trials.

SPECIFIC AIMS

Specific Aim 1: We will test the prediction that patients administered high-dose vitamin C will show clinically-significant reductions in pro-inflammatory and coagulation markers at peak response and at 48 hours relative to normal saline controls. Specifically, we will measure

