- a) Levels of circulating pro-inflammatory biomarkers profiles (CRP, IL-6, TNF- α), NGAL (in urine), and lipid pro- and anti-inflammatory mediators (in plasma);
- b) Levels of coagulation biomarker and platelet function (e.g. fibrinogen, platelet counts, thrombomodulin, R, K, MA, G, angle, LYO)

Specific Aim 2: We will test the prediction that reduced post-surgical inflammatory burden of patients administered high-dose vitamin C will result in clinically significant reductions in hospital-based outcomes (such as length of hospital stay, length of ICU stay.)

STUDY DESIGN

This is a prospective, double-blind, placebo-controlled, randomized pilot trial comparing high-dose intravenous vitamin C to placebo (normal saline) infusions in elective non-emergent cardiac bypass patients. Double blinding will be used at enrollment, randomization, and throughout treatment, sampling, analysis, and data interpretation phases.

The purpose of this pilot study is to demonstrate **performance feasibility** and **proof of concept (PoC)** before initiation of a full-fledged clinical trial. Both financial and personnel constraints limit the total patient enrollment to 24 (12 per arm). Because sample sizes are so small, hypothesis testing cannot be a central feature of this proposal. Instead, success criteria will consist of tangible and measurable performance metrics relating to trial performance and PoC. *Performance success criteria* relate to the logistics and processes involved in the execution of the study itself (e.g. recruitment, retention, study flow, operations, management, obtaining samples, sample processing, documentation, compliance oversight). *Proof of concept* will be determined by large effect size differences (20%) between test and experimental intervention groups in one or more of the key inflammation and coagulation markers (see **OUTCOMES**).

It is unethical to consider running a phase III trial without sufficient data or feasibility information. This pilot trial will be extremely useful to inform the planning and execution of the future large-scale trial, especially with respect to feasibility and sample size calculations. Proof of concept information will be essential for writing major grants, which usually require such preliminary information for assessing scientific validity²¹⁻²³

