Dose/route. **Previous studies** describing use of IV vitamin C²⁴⁻²⁶ suggests that a total dose of 200mg/kg/day administered as 4 intravenous doses in 50mL D5W every 6 hours per day for 4 days will be sufficient to permit biologically-effective plasma concentrations, and thus are hypothesized to reduce deleterious effects associated with CPB-induced

November 16, 2016

inflammation. The intervention schedule in our study was based on a general knowledge of inflammation trajectory; inflammation typically peaks during CPB itself then stabilizes within a 24-hour period²⁷. **Accordingly, in this study** intravenous Vitamin C will be given as 200mg/kg/day divided over 4 intravenous doses every 6 hours per day for only 2 days perioperative.

Completion of study drug administration: Study drug administration will be stopped when one of the following conditions is met, whichever comes first:

1. Final drug dose at 48 hours
3. Inability to obtain peripheral access after removal of central line.
4. Discharge from the hospital
5. Withdrawal from study
6. Death

ETHICAL OVERSIGHT

Prior to study initiation, this study will be approved by the Virginia Commonwealth University (VCU) Institutional Review Board, and an IND requested from the Food and Drug Administration (FDA). The trial will be registered with *ClinicalTrials.gov*, and the definitive protocol submitted for publication in one of the open-access clinical trial specific journals (e.g. *Trials*). This is an investigator-initiated study, falling under an existing IND held by another investigator who is not acting as PI. In accordance with GCP, monitoring will occur through the use of a monitor not affiliated with this study. This monitor, while employed at the institution conducting the study, has not been affiliated with the development or execution of this study.

STUDY POPULATION

The study population will consist of adult patients scheduled for elective non-emergent cardiac surgery at Virginia Commonwealth University Medical Center, and who have consented to participation in the study.

Inclusion criteria are: (1) adult (≥ 18 years) patients (2) scheduled for elective non-emergent cardiac valve replacement or repair with cardiopulmonary bypass, and/or multi-vessel CABG surgery.

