Coagulation and inflammation markers: We hypothesize that oxidative stress acquired during CPB and surgery will upregulate coagulation pathways and vitamin C administration will reduce overall expression and/or reduce the duration of the response. Coagulation testing will include RoTEM, fibrinogen, thrombomodulin, and platelet count. Fibrinogen is a liver-produced acute-phase reactant that increases as a result of inflammation. The release of soluble thrombomodulin is associated with increased pro-coagulant response. Thrombomodulin must be expressed on the endothelium to convert thrombin to an anti-coagulant. The RoTEM measures the viscoelastic properties of clot formation and fibrinolysis. Cytokines are soluble proteins acting as cell signalling and regulator molecules to coordinate generalized inflammatory responses. We will measure a few selected pro-inflammatory cytokines (e.g. IL -6, TNF- α) and non-cytokine markers such as C-reactive protein (CRP) and white blood cell counts. NGAL (neutrophil gelatinase-associated lipocalin) is a marker protein that starts to increase early (earlier than creatinine) in acute kidney injury (AKI). AKI is a very common clinical problem in cardiac surgery ICU (~40%). Both NGAL and creatinine will be followed.

Lipidomics: We hypothesize that oxidative stress acquired during CPB and surgery leads to oxidation of both substrate phospholipids and already-generated precursor molecules, such as arachidonic acid (AA). The oxidation of these lipids would deprive the eicosanoid biosynthetic enzymes of necessary precursors and effectively dysregulate the production of lipid mediators important in maintaining platelet function as well as modulating platelet/leukocyte/endothelial cell interplay. We further hypothesize that administration of high dose vitamin C will attenuate or correct these processes. We have preliminary data suggesting a time-dependent conversion of 2 AA phosphatidylcholine (2-AA-PC) to oxidized 2-AA-PC without a significant effect on total 2-AA-PC levels. This effect correlated with a dramatic reduction in the production of TXB₂. We also have data to show that co-treatment of blood with vitamin C and AA attenuates the loss of TXB₂ levels caused by oxidative stress. Thus, we are confident about the relationship between loss of lipid mediators and previously-demonstrated loss of platelet function induced by oxidative stress.

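### The proof-of-concept rule does not control false passes: an inert treatment can meet it, at a rate the plan neither limits nor allows one to derive

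*Combined protocol and SAP*

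**What the plan says.** STUDY DESIGN gives the pilot two purposes, feasibility and proof of concept. Proof of concept is decided by "large effect size differences (20%) between test and experimental intervention groups in one or more of the key inflammation and coagulation markers", with a pointer to OUTCOMES. (The second group named is presumably meant to be the control.) Enrolment is 24, 12 per arm. The same section says that "hypothesis testing cannot be a central feature of this proposal", that the pilot will inform the later trial "especially with respect to feasibility and sample size calculations", and that proof-of-concept information is needed for major grants.

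The marker lists are partly open:

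- SPECIFIC AIMS, Aim 1a names CRP, IL-6, TNF-alpha, urinary NGAL and lipid mediators. Aim 1b gives its coagulation markers as examples: "e.g. fibrinogen, platelet counts, thrombomodulin, R, K, MA, G, angle, LYO".
- OUTCOMES is firm on some items ("Coagulation testing will include RoTEM, fibrinogen, thrombomodulin, and platelet count") and open on others ("We will measure a few selected pro-inflammatory cytokines"). It does not say which markers are key.

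On direction and time, Aim 1 predicts "clinically-significant reductions in pro-inflammatory and coagulation markers at peak response and at 48 hours relative to normal saline controls". The Dose/route text says that "inflammation typically peaks during CPB itself then stabilizes within a 24-hour period", and POST-RANDOMIZATION TREATMENT labels the second draw as taken during bypass, but nothing names that draw as the peak. Urine is collected at baseline, 6 and 24 hours, so NGAL has no 48-hour value.

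DATA ANALYSES promises point estimates with 95% confidence intervals. These do not enter the 20% rule.

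**The concern.** A rule that is met when any one of several markers crosses a fixed point-estimate threshold is a decision rule with an error rate, whether or not it is called a test. With 12 per arm, a variable marker can differ by 20% through chance alone, and each further marker or eligible time point adds another opportunity. The rule limits neither. It uses no interval, no baseline adjustment and no allowance for the number of markers, and the set of markers that may count is not closed before the data are seen.

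What is at stake is the meaning of one of the pilot's two declared success criteria. If an inert treatment could often meet it, then reporting that proof of concept was met would add little to a grant application or to planning the next trial.

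**Working it through.** The plan states no alpha, power, CV or false-pass rate, so there is no figure of its own to reproduce. The check asks how often the rule is met when treatment does nothing.

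**Inputs from the documents.** 12 per arm; a 20% threshold; one or more markers (STUDY DESIGN). Aim 1 names 4 inflammation markers and 9 coagulation markers, 13 in all. The lipid panel is left out.

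**Assumptions.** Log-normal markers; only reductions count; a pass is a ratio of unadjusted arm means of 0.80 or less; between-marker correlation 0.3 to 0.6; within-marker correlation 0.6 between draws. Four CV cases: all 13 at 20%; then five markers at a higher and eight at a lower CV (30%/15%, 60%/25%, 100%/30%).

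**Step 1, one marker.** Log SD = sqrt(ln(1+CV²)); SE of the log ratio = SD × sqrt(2/12); for geometric means, chance of a null pass = Φ(ln 0.80 / SE), with ln 0.80 = -0.223.

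- CV 20%: SD 0.198, SE 0.081, z = -2.76, about 0.3%.
- CV 50%: SD 0.472, SE 0.193, z = -1.16, about 12% (13% by simulation with arithmetic means).
- CV 100%: SD 0.833, SE 0.340, z = -0.66, about 26% (28% by simulation with arithmetic means).

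**Step 2, any of 13 markers, inert treatment** (simulation, arithmetic means; ranges span the correlations):

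| CV case | One draw | Peak or 48 h | Same marker at both |
|---|---|---|---|
| all 20% | about 3% | 5-6% | under 1% |
| 30%/15% | 11-14% | 17-21% | 3% |
| 60%/25% | 43-55% | 57-69% | 20-26% |
| 100%/30% | 60-73% | 75-86% | 35-44% |

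NGAL is not counted at 48 hours. For 60%/25%, changing the between-draw correlation to 0.4 or 0.8 moves the last column to 17-21% or 27-33%. Using only the eight markers named individually in OUTCOMES, apart from RoTEM and creatinine, gives similar one-draw rates (for example 42-53% in the 60%/25% case).

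A single variable marker is enough to drive the rate. Take seven independent markers at CV 15% and one at 75%, with the normal approximation SE = CV × sqrt(2/12). The noisy marker has SE 0.306 and passes with probability 1 - Φ(0.20/0.306) = 26%. The other seven add almost nothing, so the total is 26%.

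**Step 3, does a pass separate an effect from none?** Pass rate under a true effect, divided by the null pass rate:

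- One of the more variable markers truly falls by 20%, one draw: passes 50-51% (all 20%) and 50-54% (30%/15%), against null rates of about 3% and 11-14%. The rule separates well there. In the two higher-CV cases it passes 59-69% and 68-79%, only about 1.1 to 1.4 times the null rate.
- All five more variable markers fall by 20%, one draw: about 1.3 to 1.9 times in the two higher-CV cases (for 60%/25%, 80-91% against 42-54%).
- The same five, with both time points required: about 1.7 to 3.1 times.

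**Step 4, what the interval would show at the threshold.** At an observed ratio of 0.80, the unadjusted 95% interval is exp(-0.223 ± 2.074 × SE), on 22 df: 0.68 to 0.95 at CV 20%, 0.54 to 1.19 at 50%, and 0.40 to 1.62 at 100%. The rule is met in all three, although the last two intervals include no effect.

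**The case against.** The strongest reply is that this is a declared pilot. STUDY DESIGN puts hypothesis testing aside, STUDY POPULATION says power calculations are not appropriate, LIMITATIONS OF PROPOSED RESEARCH says significance should not be emphasised, and DATA ANALYSES will show the intervals. The decision list in FUTURE RESEARCH is mostly about feasibility and does not cite the 20% rule. All of this stands, and it limits the consequence. It does not remove the point: the plan replaces testing with a pass/fail criterion, and that criterion ignores the intervals.

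A second reply is that Aim 1 supplies direction and two time points, and that its plain wording asks for both. Read that way, the false-pass rates are much lower, as the last column of the table shows. This also stands. But the rule itself does not repeat the requirement, and no draw is identified as the peak.

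A third reply concerns the model. All CVs are assumed, and clot-function parameters are treated like cytokines, although the documents do not establish that a fall in each one is the predicted benefit. The similar result with the eight-marker set suggests that this matters little numerically, but the 13-marker model is an illustration and not Aim 1's rule.

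A reader might also infer that a pass is weak evidence in general. The documents do not support that. The 1.1 to 1.4 contrast assumes exactly one truly reduced marker and one draw, whereas the protocol hypothesises an upstream effect and reductions in several markers.

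**Conclusion.** The concern holds in this form: the rule does not control false passes, and the chance that an inert treatment meets it cannot be derived from the documents. Confidence is high on that statement and attaches to no single rate. Under the stated assumptions the rate spans under 1% to 86%, depending on CVs, correlation and how the time points are read. With uniformly low variability the rule works acceptably. With some variable markers, its ability to separate effect from no effect ranges from poor to moderate, according to how many markers respond and whether both time points are required.

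Two stronger readings are not supported. One is that the false-pass rate is known to be high: no CV is given, and the low-CV cases are favourable. The other is that the main trial will be sized on whichever marker passes: the plan says only that the pilot will inform sample size calculations. The effect is limited to the proof-of-concept claim and its use in grants and planning. It should be fixed, because the repair is only wording.

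**What to change.** Amend the wording before unblinding.

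**Preferred: no gate.** Label proof of concept as descriptive and remove the pass/fail wording. For each marker, report the ratio of geometric means from ANCOVA on log values, adjusted for the baseline sample already planned, with its 95% confidence interval beside the 20% target. This agrees with the plan's own statements on testing, intervals and significance.

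**If a gate is kept.** Name one marker, one draw and the expected direction; for NGAL, use a time at which urine is collected. Keep the 20% point-estimate condition and add a pre-stated one-sided confidence limit that excludes no effect. The 20% condition is needed because, at CV 20%, a 90% limit alone could be met by an observed reduction of only about 7-10%. If more than one marker may pass, control the overall null rate: three markers with Bonferroni (96.7% limits) hold it at 8-10%. State the rule's null pass rate and report all other markers descriptively.

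**Cost.** No new samples, assays or patients. The descriptive option gives no pass/fail statement. With a gate, proof of concept is harder to declare. For one marker with a one-sided 90% limit alone (null rate 10%, baseline correlation 0 to 0.7), a true 20% reduction passes about 43-62% of the time at CV 50% and 26-35% at CV 100%. Keeping the 20% condition can only lower these. A true reduction of exactly 20% then passes at most about half the time, since the estimate falls on either side of 0.80 equally often.

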Approximately 20 mL of blood - 2 Na citrate tubes and 1 SST tube - will be needed to run assays described below. In addition, 3 urine samples will be collected, 5 mL each, at Baseline, 6hr, and 24 hrs. Blood and urine tubes will be transported to the analysis research lab by a study personnel member.

DATA STORAGE AND MANAGEMENT

Confidentiality will be maintained by storing paper-based records in a secure central location with access provided only to the study staff. All records will be de-identified and data coded with the key stored in a separate secure location. All personal identifying information will be kept in password protected files and these files will be deleted after 6 years, per VCU requirements. Other de-identified records, such as lab results, will be kept in a locked file cabinet for 6 years after the study ends and will be destroyed at that time. No data will be stored indefinitely.

Patients will be screened, recruited, and consented in a private exam room prior to their scheduled surgery. Collection of identifiable information will only be necessary to link the subject to medical records and/or subject data. Personal information about subjects may be shared with or copied by authorized officials of the Federal Food and Drug Administration and Department of Health and Human Services if required. Although results of this research may be presented at meetings or in publications, no identifiable personal information will be disclosed.

DATA SAFETY MONITORING BOARD (DSMB) AND SAFETY OVERSIGHT

November 16, 2016

An independent DSMB has been appointed to oversee safety monitoring and trial data comprised of physicians and a biostatistician who are not directly involved with the study and interventions.

PROTOCOL ADHERENCE

Deviations from study protocol will be reported by the Trial Coordinator to the PI and, as needed, to the VCU IRB.

ADVERSE EVENTS AND/OR DRUG REACTIONS

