Very few side effects have been observed in clinical trials of intravenous high-dose vitamin C.¹⁴ The only known reported toxicity of Vitamin C originates after continuous (days to weeks) of infusions or intake, resulting in the formation of oxalate renal calculi.¹² Another potential concern is the hypothesized pro-oxidant property of high dose Vitamin C; however, evidence supporting this claim is weak; antioxidant properties at even higher doses were demonstrated to be predominant over pro-oxidant properties.³² The safety of the proposed dose has been verified in our preliminary human data, and the safety of higher doses has previously been verified in cancer trials.³³ Overall, high-dose IV Vitamin C is regarded as having a good safety profile with a low risk of toxicity over a wide range of doses.

High-dose vitamin C levels can lead to a false reading of blood glucose levels using point of care testing. Blood glucose levels are to be measured in the metabolic lab as detailed below in the Glucose Monitoring Plan section.

GLUCOSE MONITORING PLAN:

Ascorbic acid is known to artefactually **raise** POC blood glucose readings; however, it does not raise blood glucose readings from a basic metabolic panel (BMP). Thus, extreme care must be taken to assure an accurate blood glucose level from a metabolic laboratory before initiating any insulin therapy, including sliding scale or scheduled insulin.

Guidance for blood glucose monitoring in patients enrolled this study:

- Critical care Nursing and Physician leadership at all study sites must be informed of vitamin C's effect on point of care (glucometer) blood glucose and arterial blood gas glucose point of care values.
- In-service training will be documented in the Study Training Log
- Bold signage will be displayed on all study instructions, data collection forms, and at the patient's head of bed, stating:
 - STOP! This patient is enrolled in a study with Vitamin C, which artefactually increases POC glucose testing
 - Do NOT use Accucheck or other Point of Care devices to measure glucose on this patient

November 16, 2016

- ↗ Use ONLY metabolic glucose screening performed by central laboratory as ordered in Cerner
- ↗ Do NOT initiate or utilize sliding scale, scheduled insulin, or continuous insulin infusion without laboratory confirmation of blood glucose level

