- Those receiving insulin infusion or sliding scale insulin will have metabolic glucose screening on the schedule determined by the primary physician and paid for by the study
- Blood glucose monitoring for insulin administration guidance should *only* be by a metabolic laboratory measured blood glucose results, whether or not the study patient is receiving insulin
- To accommodate the required glucose monitoring via the metabolic lab, each subject will have a dedicated peripheral line
- Study personnel will follow each study patient closely to monitor insulin use to ensure that point of care glucose screening is suspended for the research subject.
- If subject loses central venous access (PICC line and arterial line acceptable), Vitamin C infusions are to stop but subject not withdrawn. Data will be collected through end of study.
- Point of care glucose testing may resume 36 hours after the last infusion of study drug.

ADVERSE EVENT REPORTING/SAFETY REPORTING

Investigators will determine daily if any clinical adverse experiences occur during the period from informed consent through study hour 48 and will be followed up through resolution, resolved with sequelae, unresolvable or death.

It is expected that diseases/illnesses/symptoms associated with the study population will occur in the study population, independent of investigation product exposure. These associated diseases/illnesses/symptoms will be considered as part of the study inclusion processes and/or study assessments and as such will not be considered 'reportable' Adverse Events (AE)/Serious Adverse Events (SAE) unless the Investigator has a reasonable doubt regarding the relatedness of the event to the investigational product.

The investigator will evaluate any changes in laboratory values and physical signs and will determine if the change is clinically important and different from what is expected in the course of treatment of the study patients. If clinically important and unexpected adverse experiences occur, they will be recorded on the adverse event case report form.

The following will be considered reportable adverse events:

For this trial, a *reportable adverse event* is defined as:

November 16, 2016

1. Any clinically important untoward medical occurrence in a patient receiving study drug or undergoing study procedures which is different from what is expected in the clinical course of a patient undergoing cardiac bypass surgery, or,

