LIMITATIONS OF PROPOSED RESEARCH

Small sample size. This is a pilot study designed to assess feasibility and proof of concept; constraints due to restricted funding limited the scope of this initial trial. Because this is a pilot trial, statistical significance cannot and should not be emphasized in determining clinical relevance and significance of findings as this trial is not powered to detect minimal differences between groups.²²

Missing markers. Preliminary subsets of biomarkers were carefully chosen according to biological relevance, greatest relevance to cardiovascular conditions, and published strong associations with clinical outcomes. Nevertheless, relatively few biomarkers will be screened, so it is possible the relevant features of the inflammatory response may not be captured, and/or sufficient alteration in the inflammatory profile may not occur to allow discrimination between test interventions. However, the sensitivity of TA1 is optimized to the femto-molar range for most analytes. If this is not sufficient to detect much lower

November 16, 2016

concentrations present at early stages of the post-operative inflammatory response (as indicated by sample analyses and mathematical modeling) we will employ a charge reversal derivatization for detecting sub-low limit of quality level of oxilipins and free fatty acids.^{36,37}

[figure not shown]
Misidentified markers. Possible sample contamination may result in some non-lipid metabolites being misidentified as important markers. Analytes will be checked for conformity to identification parameters of experimental or theoretical lipid databases.

FUTURE RESEARCH

Pilot study results will be used to determine if proceeding to a large, adequately-powered, main trial is feasible. There are four possible feasibility outcomes:²²

- a) **Stop:** Main study not feasible (because of poor recruitment retention, staffing, insufficient resources, or high probability of treatment futility);
- b) **Continue, but modify protocol:** Feasible with modifications (most likely scenario; this could include modifications of operational logistics, dose loads, dosing schedules, data acquisition protocols, etc.);
- c) **Continue without modifications, but monitor closely** (for example, if the major limitation is ensuring patients get the appropriate test intervention at the appropriate time, we could have in-place monitor);
- d) **Continue without modifications:** feasible as is.

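### The two rules on loss of vascular access are not aligned: with only peripheral access left, the stopping list implies that study drug continues, while the glucose plan says it stops

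*Combined protocol and SAP*

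**What the plan says.** Three parts of the protocol bear on this.

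- **Completion of study drug administration** (under STUDY DESIGN). The list opens: "Study drug administration will be stopped when one of the following conditions is met, whichever comes first". The only access condition that can be read in it is item 3: "Inability to obtain peripheral access after removal of central line". Removal of the central line is not in itself a visible stop. The list as available runs 1, 3, 4, 5, 6. Item 2 cannot be seen, and its absence is not held against the plan.
- **GLUCOSE MONITORING PLAN.** The access rule here is: "If subject loses central venous access (PICC line and arterial line acceptable), Vitamin C infusions are to stop but subject not withdrawn". It makes no exception for a working peripheral vein. The same section adds "Point of care glucose testing may resume 36 hours after the last infusion of study drug" and "To accommodate the required glucose monitoring via the metabolic lab, each subject will have a dedicated peripheral line". Its reason is that vitamin C falsely raises point-of-care glucose readings, so that "extreme care must be taken to assure an accurate blood glucose level from a metabolic laboratory before initiating any insulin therapy".
- **Where doses are given and when lines come out.** INTERVENTION AND CONTROLS has step-down units giving study drug as well as the ICU. ETHICAL CONSIDERATIONS allows for the arterial and central lines being out before hour 48. Enrollment Goal 4 under OUTCOMES asks that all 24 patients receive every scheduled dose.

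**The concern.** Item 3 stops dosing when a peripheral vein cannot be found after the central line is out. The natural inference is that someone looks for a peripheral vein and uses it if there is one. The glucose plan stops the infusion in that same patient once no PICC or arterial line is left either. Nothing says which rule governs, and a nurse working from the stopping list has no reason to look for a further stop in a section on glucose.

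The patient is foreseeable, since the protocol expects both early line removal and dosing on step-down units. What is at stake is that study drug could be given, in good faith, where the safety section says it should not be. Each such dose also postpones the return to point-of-care glucose testing by six hours. Until then, insulin may be guided only by laboratory glucose.

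**Working it through.** **Step 1: apply both rules to each access state.** The plan has no figure of its own to reproduce.

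| Lines remaining | Stopping list, item 3 | Glucose plan | Agree? |
|---|---|---|---|
| None of central, PICC, arterial; peripheral vein works | No access stop met; continuing is implied | Stop | No |
| Central out; PICC or arterial in; peripheral vein works | Continue | Continue | Yes |
| None of the three; no peripheral vein | Stop | Stop | Yes |
| Central out; PICC or arterial in; no peripheral vein | Stop | No stop required | Differ |

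The first row is the point at issue. The last row shows that item 3 keeps a use even if the rules are meant to be cumulative, for example with an arterial line in place but no vein for the infusion.

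**Step 2: inputs for the size per patient.**

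- Four doses a day for two days (INTERVENTION AND CONTROLS): 4 × 2 = 8 doses. Check on volume: 8 × 50 mL = 400 mL, which matches the stated total of about 400 mL.
- Assumed schedule: doses at hours 0, 6, ..., 42, with infusion time ignored.
- Point-of-care testing resumes 36 hours after the last infusion (GLUCOSE MONITORING PLAN).

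**Step 3: formulas.** Suppose all three lines are lost after dose k and before dose k + 1.

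- Last dose under the glucose plan: hour 6(k − 1).
- Point-of-care testing resumes at hour 6(k − 1) + 36.
- Full course (k = 8): last dose at hour 42, testing from 42 + 36 = hour 78.
- Further doses if dosing continues by peripheral vein: 8 − k.
- Added laboratory-only hours: 78 − [6(k − 1) + 36] = 6(8 − k).

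| Lines lost (hours) | Doses if stopped | Further doses if continued | Testing resumes if stopped | Added hours if continued |
|---|---|---|---|---|
| 18–24 | 4 | 4 | 54 | 24 |
| 24–30 | 5 | 3 | 60 | 18 |
| 30–36 | 6 | 2 | 66 | 12 |
| 36–42 | 7 | 1 | 72 | 6 |
| after 42 | 8 | 0 | 78 | 0 |

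Loss before hour 18 would give larger differences by the same formula.

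**Step 4: sensitivity.** Item 1 of the stopping list places the final dose at 48 hours. If a dose is given then as well, there are 9 doses (9 × 50 = 450 mL, a poorer fit to about 400 mL). The full course then ends laboratory-only glucose at 48 + 36 = hour 84. Each added figure rises by 6 hours (30 instead of 24 in the first row), and line loss between hours 42 and 48 also makes a difference of 6 hours.

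**Frequency.** The documents give no line-removal times or rates, so the number of affected patients cannot be estimated.

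**The case against.** The strongest reply is that the instructions do not contradict each other. The stopping list says when to stop; nowhere does it order continued peripheral dosing. The glucose plan gives an express stop. Staff can obey both by stopping when either condition is met, and the unseen item 2 might even cover central access. This stands as far as it goes: a reader might infer an outright contradiction, and the text does not support that. But the cumulative reading is stated nowhere, and item 3 still suggests that a peripheral vein is to be sought. A central-access stop in item 2 would sit awkwardly beside it.

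The glucose risk is also limited. Laboratory-only glucose to hour 78 is the planned restriction for every full-course patient, so continuing does not take a patient beyond it. The dedicated peripheral line is there for laboratory sampling. Known diabetes is an exclusion criterion, which reduces insulin use.

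Three stronger readings are tempting and should not be drawn:

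- *A withheld dose would be a deviation under the stopping list.* It would not. A dose withheld under an express stop elsewhere in the same protocol is compliant; only the peripheral dose is a candidate deviation.
- *A shortfall on Goal 4 could not be classified.* Doses are prompted through the electronic record, and PROTOCOL ADHERENCE states "Deviations from study protocol will be reported by the Trial Coordinator to the PI". Loss of access can be established as a reason whichever rule was followed.
- *The misalignment costs exposure and Goal 4 completion.* Fewer doses, and the loss of a patient from Goal 4, follow from the glucose plan's rule itself, which the fix keeps. They do not measure this defect.

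**Conclusion.** The point holds as a minor one. In one foreseeable kind of patient (no central, PICC or arterial line, but a working peripheral vein), the stopping list implies dosing that the glucose plan stops, and the protocol does not say which governs. On the assumed eight-dose schedule, loss of all three lines between hours 18 and 24 makes a difference of up to 4 doses and 24 hours of laboratory-only glucose. The difference shrinks to 1 dose and 6 hours for loss between hours 36 and 42, and to nothing after that.

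The conclusion rests on item 3 implying peripheral dosing and on the list as it can be read without item 2. A reader might infer a threat to the treatment comparison. The documents do not support that: bags are indistinguishable, so both arms are affected alike, and data collection continues after a stop. No sample-size or power figure is involved.

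**What to change.** Put one rule, worded identically for blinded study drug in both arms, in Completion of study drug administration (replacing item 3) and in the GLUCOSE MONITORING PLAN (replacing the present sentence on loss of central access). Default to the stricter existing rule:

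> *Study drug stops when no central, PICC or arterial line remains, or when no venous route for the infusion can be obtained. The participant is not withdrawn, and data collection continues to the end of the study.*

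This settles both rows of the table in which the rules differ. Record the reason for each dose not given, and in Goal 4 report doses not given under this rule separately from missed doses.

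The cost is wording in two sections, an update to the in-service training and one recorded reason per dose not given. The downside is that some patients will receive fewer than eight doses, which is already so under the glucose plan. If the sponsor prefers peripheral dosing after all three lines are lost, that relaxes a stop rule and would need safety and IRB review.
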